#### Timeline for the analysis

All analyses are to be performed after the SAP has been published on ClinicalTrials.gov (NCT04614207).

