### Protocol deviations

Due to the COVID-19 pandemic and related shutdown of schools and after school activities, data collection was hindered and thus resulted in a reduced number of expected participants. Thus, deviations to protocol (as published (1), and initially registered at ClinicalTrials.gov November 3, 2020) are as follows:

- Data collection ended January 31st 2022
- It is not a requirement for the children to be registered in the CPUP
- Primary analysis: Due to a relatively large amount of included children not being registered in the CPUP, additional analyses will be performed on all children with accelerometry data (Model 1b):
  - o Model 1
    - a) Multiple linear regression analysis between accelerometer counts (response variable) and all CPUP variables within each ICF component (predictive variables), using the latest CPUP registration prior to accelerometer data collection.
    - b) Multiple linear regression analysis between accelerometer counts (response variable) and all questionnaire variables within each ICF component (predictive variables), using the questionnaire data.
- Secondary analysis. Due to the limited amount of children and adolescents included in the study, the protocol's model 2a (backward stepwise regression with accelerometer counts as the response variable and all included CPUP variables as predictive variables) will be performed for both model 1a and 1b using penalized regression. Furthermore, the initial model 2b (Multiple linear regression analysis between accelerometer counts (response variable) and all included variables as predictive variables) will be eliminated:
  - o Model 2
    - a) Penalized regression (lasso) with accelerometer counts as the response variable and covariates as chosen by lasso to obtain an optimal fit from model 1a as predictive variables to determine which variables to retain in the model.
    - b) Penalized regression (lasso) with accelerometer counts as the response variable and covariates as chosen by lasso to obtain an optimal fit from model 1b as predictive variables to determine which variables to retain in the model.

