### Missing data

Missing outcome data (accelerometer data) will exclude the child from the study population. Missing data on predictors (CPUP and questionnaire data, including personal factors) will be handled by multiple imputation by multivariate imputation using chained equation (MICE) including all predictors and 100 imputation samples.

In model 2a and 2b the imputation will be performed before applying the lasso, and afterwards the predictors will be ordered by proportion of imputation sets in which they are included. From this prioritized list, we will construct a final prediction model including all predictors included in at least 50% of the

imputation sets, but other cutoffs than 50% will be evaluated by an elbow plot, and if a different cutoff appears convincing from the plot, this cutoff will be applied.

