Table 3. Prediction of physical activity using questionnaires as predictive variables (Model 1b)

ICF constructs	Variables	Coef. [95% CI]	p-value	Adj.R 
Body Function & Structure				xx
	ROM	xx [xx,xx]	xx	
	Number of hours of sleep per night	xx [xx,xx]	xx	
	GMFCS level	xx [xx,xx]	xx	
	PODCI – pain/comfort scale	xx [xx,xx]	xx	
Activities				xx
	FMS (5m, 50m 500m)	xx [xx,xx]	xx	
	Means of transport to school	xx [xx,xx]	xx	
	Hours of screen time per day	xx [xx,xx]	xx	
Participation				xx
	Participation in PT at school	xx [xx,xx]	xx	
	Participation in recreational activities	xx [xx,xx]	xx	
	PODCI - Global Function score	xx [xx,xx]	xx	
	PODCI - Sports and Physical Functioning score			
Personal Factors				xx
	Age	xx [xx,xx]	xx	
	Gender	xx [xx,xx]	xx	
	Parent's educational level	xx [xx,xx]	xx	
Environmental Factors				xx
	Residence region	xx [xx,xx]	xx	
Quality of Life				xx
	PedsQL	xx [xx,xx]	xx	

Abbreviations: ROM: Range of motion; FMS: Functional Mobility Scale, PODCI: Pediatric Outcomes Data Collection Instrument; PT: physical training; PedsQL: Pediatric Quality of Life Inventory, CP Module

Table 4. Prediction model using “the best” CPUP variables (penalized regression, lasso) (model 2a)  
(Like table 2, only including the variables that the lasso regression has selected)

Table 5. Prediction model using “the best” questionnaire variables (penalized regression, lasso)  
(model 2b)

(Like table 3, only including the variables that the lasso regression has selected)

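### In secondary Models 2a and 2b, the 50% retention cutoff can be replaced by eye after the lasso results are known, with no stated criterion and no duty to show the 50% model

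*Combined protocol and SAP*

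**What the plan says.** Section 7, Missing data, sets the order of steps for Models 2a and 2b. Predictors are imputed 100 times and the lasso is applied. Then "afterwards the predictors will be ordered by proportion of imputation sets in which they are included". The default, in which the percentage refers to imputation sets, is stated as follows: "we will construct a final prediction model including all predictors included in at least 50% of the". This default is qualified at once. Alternative thresholds are to be examined graphically with an elbow plot, and the same sentence ends with the override: "if a different cutoff appears convincing from the plot, this cutoff will be applied".

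The output shells are in section 8. Table 4 is described as "Like table 2, only including the variables that the lasso regression has selected", and Table 5 as "Like table 3, only including the variables that the lasso regression has selected". Each provides for one model.

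Two other places bear on the weight of the point. Section 4, Protocol deviations, introduces the lasso models under "Secondary analysis. Due to the limited amount of children and adolescents included in the study", so they are secondary. Section 3, Timeline for the analysis, says "All analyses are to be performed after the SAP has been published on ClinicalTrials.gov", so the 50% default is on public record before any result exists.

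**The concern.** The override acts after the lasso has used the accelerometer outcome and after the analyst can see which predictors fall on each side of every possible cutoff. The SAP does not define the axes of the plot, the range of cutoffs considered, what counts as an elbow, or who judges it. Two analysts who follow the text faithfully could publish different final models from the same data.

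The study aims to identify predictors of habitual physical activity, and Model 2 exists to decide which variables stay. The list of retained predictors is therefore the result of this analysis, and it is what the override can change. A reader could notice a departure from the public 50% rule, but might have no way to see what that rule gave. The layouts carried over from Tables 2 and 3 include coefficients, confidence intervals, p-values and adjusted R-squared, so a visually chosen model would look the same as one fixed in advance.

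**Working it through.** The SAP gives no power or error figure that depends on the cutoff, so there is no figure of its own to reproduce. The defect rests on the text. The simulation only shows how much a change of cutoff could matter.

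**How many models are open.** Table 2 has 4 + 4 + 2 + 3 + 3 = 16 candidate rows and Table 3 has 4 + 3 + 4 + 3 + 1 + 1 = 16. Counting each row as one predictor, the ranked list allows up to 16 nested non-empty models for each analysis. A fixed cutoff leaves one, once the lasso penalty is also fixed.

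**Inputs from the SAP.** n = 78 (CPUP data) and n = 123 (accelerometer data), from Study size; 16 predictors, from the table rows; 100 imputations, from Missing data.

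**Assumptions.**
- Pairwise correlation 0.2.
- 8 of the 16 predictors incomplete, missing completely at random, at 2%, 10% or 20%.
- Signal A: R-squared 0.20 with 3 true predictors. Signal B: R-squared 0.40 with 5.
- Penalty by 10-fold cross-validation (same folds in all imputed sets) or by BIC.
- Chained normal regressions on the predictors only, 8 cycles.
- 100 datasets per scenario.

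Cutoffs are compared directly; no elbow is modelled. Ranges run over signal, n and penalty method.

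| | 2% missing | 10% missing | 20% missing |
|---|---|---|---|
| Mean predictors added, 50% to 30% | 0.2-0.7 | 0.5-1.1 | 0.6-1.5 |
| Mean predictors removed, 50% to 90% | 0.6-1.1 | 0.7-2.1 | 0.7-2.9 |
| 30% and 50% models differ | 13-33% | 33-66% | 39-79% |
| 50% and 70% models differ | 12-33% | 23-57% | 25-73% |
| 30%, 50% and 70% all agree | 45-77% | 14-54% | 9-44% |

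The first two rows are differences in mean model size. The end points at 10% missing are:
- Added, smallest (n = 78, signal A, BIC): 2.35 - 1.81 = 0.54.
- Added, largest (n = 78, signal A, cross-validation): 6.70 - 5.59 = 1.11.
- Removed, smallest (n = 123, signal A, BIC): 2.29 - 1.55 = 0.74.
- Removed, largest (n = 78, signal B, cross-validation): 8.08 - 5.97 = 2.11.

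With 100 datasets, the Monte Carlo standard error of a percentage is at most √(0.5 × 0.5 / 100) = 5 points.

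**Several terms per row.** Giving region, GMFCS level and FMS or CP subtype several terms each (22 terms in all, 10% missing) gives 0.49-1.16 added and 0.72-2.24 removed, close to the figures above. Splines and interactions, which the SAP also allows, are not modelled.

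**Fit.** Mean apparent adjusted R-squared at 30% or 70% is within 0.03 of the 50% model. At 90% it is up to 0.08 lower.

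**A second, smaller simulation** used other assumptions: correlation 0.3, four true effects, every predictor subject to 10% or 25% missingness, 5-fold cross-validation with folds redrawn for each imputed set, 20 imputations and 10 datasets per setting. At 10% missing, moving from 50% to 30% added 9.2 - 6.9 = 2.3 predictors at n = 78 and 9.4 - 8.0 = 1.4 at n = 123. Between 30% and 80% the model changed in every dataset, by a median of 4 to 5.5 predictors depending on the setting.

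**The case against.** The strongest reply is that this is a pre-specified rule with a judgement step. The SAP names a numerical default, a ranking and a tool in advance, and elbow plots are usually read by eye. That is correct, and it limits the charge: the flaw is a subjective, results-dependent override, not the absence of a rule. The 50% value is itself a convention.

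The simulation compares fixed cutoffs, so it does not measure how the override would behave, and missingness, which drives the figures, is not given in the documents. That also stands. The two simulations disagree in size at 10% missing (0.5-1.1 predictors against 1.4 and 2.3), so the figures depend on the assumptions. The second had only 10 datasets per setting, and its difference is towards a larger effect.

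The choice of penalty matters more. At the 50% cutoff, cross-validation and BIC differ by 2.4 to 4.3 predictors (for example 8.39 - 5.95 = 2.44 and 6.10 - 1.80 = 4.30). The SAP names no penalty criterion and specifies seeds only for imputation. Fixing the cutoff therefore does not by itself make the final model reproducible. The unnamed penalty is a separate gap, and it makes the gain here partial but still real.

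The consequence is narrow: the models are secondary, fit barely moves between nearby cutoffs, and nothing forbids showing the 50% model. Similar fit does not settle the matter, however. It leaves little objective ground for preferring one nearby cutoff while the named predictors change.

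**Conclusion.** The concern holds. The SAP lets a visual judgement, made after the outcome has been used, replace its published cutoff, and it does not require what that cutoff gave to be shown. The text establishes this without the simulation.

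Under the main simulation's assumptions, the choice between 30% and 50% changes the reported model in about 13-79% of datasets, and less often when few data are missing. In 9-77% of datasets the 30%, 50% and 70% cutoffs agree and the choice among them makes no difference. These percentages show how often the model depends on the cutoff, not how often the override would be used. Model 1 is unaffected. The point should be corrected before analysis, but it does not threaten the primary results.

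**What to change.** In Missing data, replace the override clause with: *The final model contains the predictors selected in at least 50% of the 100 imputation sets; all inclusion proportions, the elbow plot and models at other cutoffs are reported as sensitivity analyses only.*

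The cost is one SAP sentence and a supplementary table or figure. No new data are needed and no other figure in the SAP changes. The sponsor gives up the option of making an elbow-based cutoff the final model. Fixing 50% does not remove predictors selected by chance; the gain is pre-specification and transparency.

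If the sponsor wishes to keep the elbow, the alternative is a numerical elbow rule with the plot defined before analysis, and the inclusion proportions, the plot and the 50% model always reported beside the chosen one.

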### Adverse events

Measuring habitual PA by accelerometry is a non-invasive method commonly used in research and has no known risks or side effects. However, should there be any reports of adverse events then these will be reported.

### Statistical software

All statistical analyses will be performed using Stata/IC 17 or later for Windows (Stata-Corp LLC, College Station, TX, USA). Random seeds will be specified for imputation.

## 8. Supplementary information

### SAP tables and figures

[figure not shown]

Figure 1. Flowchart of participants

Table 1. Participant characteristics

	Participants with CPUP data (n= )	Participants without CPUP data (n= )	Non-participants from CPUP (n= )
Age in years (mean (SD))			
At index date	xx (xx)	xx (xx)	xx (xx)*
Time in months from index date (mean (SD))			
To collection of questionnaire data	xx (xx)	xx (xx)	-
To collection of accelerometer data	xx (xx)	xx (xx)	-
To collection of CPUP data	xx (xx)	-	xx (xx)
Gender (n (%))			
Boy	xx (%)	xx (%)	xx (%)
Girl	xx (%)	xx (%)	xx (%)
Region of residence (n (%))			
Capital Region of Denmark	xx (%)	xx (%)	xx (%)
Central Denmark Region	xx (%)	xx (%)	xx (%)
Region of Northern Denmark	xx (%)	xx (%)	xx (%)
Region Zealand	xx (%)	xx (%)	xx (%)
Region of Southern Denmark	xx (%)	xx (%)	xx (%)
Cerebral palsy subtype (n (%))			
Spastic	xx (%)	-	xx (%)
Ataxic	xx (%)	-	xx (%)
Dyskinesia	xx (%)	-	xx (%)
Mixed/not classified	xx (%)	-	xx (%)
Missing data	xx (%)	-	xx (%)
GMFCS level (n (%))			
I	xx (%)	xx (%)**	xx (%)
II	xx (%)	xx (%)**	xx (%)
III	xx (%)	xx (%)**	xx (%)
Accelerometer count (mean (SD))	xx (xx)	xx (xx)	-

Abbreviations: GMFCS: Gross Motor Function Classification System, CPUP: Cerebral Palsy Follow-Up Program

Index date= date on which consent was given for participation, \*= the time of mass release of invitation to the study (November 3, 2020), \*\*=as reported by parents

Table 2. Prediction of physical activity using CPUP data predictive variables (Model 1a)

ICF constructs	Variables	Coef. [95% CI]	p-value	Adj.R 
Body Function & Structure				xx
	ROM	xx [xx,xx]	xx	
	Pain	xx [xx,xx]	xx	
	Muscle tone (modified Ashworth Scale)	xx [xx,xx]	xx	
	GMFCS level	xx [xx,xx]	xx	
Activities				xx
	FMS	xx [xx,xx]	xx	
	GMFM-66 score	xx [xx,xx]	xx	
	Ability to climb stairs	xx [xx,xx]	xx	
	Bikes	xx [xx,xx]	xx	
Participation				xx
	Participation in PT at school	xx [xx,xx]	xx	
	Participation in recreational activities	xx [xx,xx]	xx	
Personal Factors				xx
	Age	xx [xx,xx]	xx	
	Gender	xx [xx,xx]	xx	
	CP classification	xx [xx,xx]	xx	
Environmental Factors				xx
	Residence region	xx [xx,xx]	xx	
	Use of orthosis	xx [xx,xx]	xx	
	Use of wheelchair	xx [xx,xx]	xx	

Abbreviations: ROM: Range of motion; FMS: Functional Mobility Scale, PODCI: Pediatric Outcomes Data Collection Instrument; PT: physical training;

Table 3. Prediction of physical activity using questionnaires as predictive variables (Model 1b)

ICF constructs	Variables	Coef. [95% CI]	p-value	Adj.R 
Body Function & Structure				xx
	ROM	xx [xx,xx]	xx	
	Number of hours of sleep per night	xx [xx,xx]	xx	
	GMFCS level	xx [xx,xx]	xx	
	PODCI – pain/comfort scale	xx [xx,xx]	xx	
Activities				xx
	FMS (5m, 50m 500m)	xx [xx,xx]	xx	
	Means of transport to school	xx [xx,xx]	xx	
	Hours of screen time per day	xx [xx,xx]	xx	
Participation				xx
	Participation in PT at school	xx [xx,xx]	xx	
	Participation in recreational activities	xx [xx,xx]	xx	
	PODCI - Global Function score	xx [xx,xx]	xx	
	PODCI - Sports and Physical Functioning score			
Personal Factors				xx
	Age	xx [xx,xx]	xx	
	Gender	xx [xx,xx]	xx	
	Parent's educational level	xx [xx,xx]	xx	
Environmental Factors				xx
	Residence region	xx [xx,xx]	xx	
Quality of Life				xx
	PedsQL	xx [xx,xx]	xx	

Abbreviations: ROM: Range of motion; FMS: Functional Mobility Scale, PODCI: Pediatric Outcomes Data Collection Instrument; PT: physical training; PedsQL: Pediatric Quality of Life Inventory, CP Module

Table 4. Prediction model using “the best” CPUP variables (penalized regression, lasso) (model 2a)  
(Like table 2, only including the variables that the lasso regression has selected)

Table 5. Prediction model using “the best” questionnaire variables (penalized regression, lasso)  
(model 2b)

(Like table 3, only including the variables that the lasso regression has selected)

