## 4. Statistical principals

### Confidence intervals and p-values

The significance level for statistically significant differences will be set at an  $\alpha = 0.05$  level (two-tailed testing) and will be presented as means and 95% confidence interval unless stated otherwise.

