#### **Regression models**

Models will be checked using graphic inspection of diagnostic plots. Splines will be used to account for non-linear effects, and interactions will be included in the model based on relevant subject-matter knowledge. The coefficient of determination, adjusted R-squared, will illustrate the percentage of variance in PA that is explained by the predictive variables. The higher the coefficient, the stronger the relationship. The root mean squared error of the estimate will indicate the accuracy of the predictions.

The following models will be applied:

- Model 1
  - a) Multiple linear regression analysis between accelerometer counts (response variable) and all CPUP variables within each ICF component (predictive variables), using the latest CPUP registration prior to accelerometer data collection.
  - b) Multiple linear regression analysis between accelerometer counts (response variable) and all questionnaire variables within each ICF component (predictive variables), using the questionnaire data.
- Model 2
  - a) Penalized regression (lasso) with accelerometer counts as the response variable and covariates as chosen by lasso to obtain an optimal fit from model 1a as predictive variables to determine which variables to retain in the model.
  - b) Penalized regression (lasso) with accelerometer counts as the response variable and covariates as chosen by lasso to obtain an optimal fit from model 1b as predictive variables to determine which variables to retain in the model.

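### Tables 4 and 5 show 95% CIs and p-values for lasso-selected predictors with no allowance for the selection

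*Combined protocol and SAP*

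**What the plan says.** - **Table shells (Section 8, SAP tables and figures).** Tables 2 and 3 have columns for the coefficient with its 95% CI, the p-value and adjusted R-squared. Tables 4 and 5 are not drawn. Table 4 is described as "Like table 2, only including the variables that the lasso regression has selected" and Table 5 as "Like table 3, only including the variables that the lasso regression has selected".
- **Role of the lasso (Section 7, Regression models).** Model 2a uses "covariates as chosen by lasso to obtain an optimal fit from model 1a as predictive variables to determine which variables to retain in the model"; Model 2b does the same from Model 1b. The response is accelerometer counts.
- **Status (Section 4, Protocol deviations).** The lasso replaces the protocol's stepwise model, in the entry that begins "Secondary analysis. Due to the limited amount of children and adolescents included in the study".
- **Retention rule (Section 7, Missing data).** Imputation is by "chained equation (MICE) including all predictors and 100 imputation samples". The lasso is then run in each imputed set, and "we will construct a final prediction model including all predictors included in at least 50% of the" imputation sets. The cutoff may be changed after an elbow plot is inspected.
- **Error level (Section 4, Confidence intervals and p-values).** "The significance level for statistically significant differences will be set at an" alpha of 0.05 "level (two-tailed testing) and will be presented as means and 95% confidence interval unless stated otherwise". Model 2 is not excepted.

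The SAP does not say how CIs or p-values in Tables 4 and 5 are obtained or how they should be read.

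**The concern.** A variable enters Table 4 or 5 because it looked related to the outcome in these children. Testing it again on the same children, as though it had been named in advance, uses the same evidence twice. The 100 imputed sets do not cure this: they deal with missing predictor values, and every set contains the same children with the same outcomes.

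The study's stated objective is to identify predictors of habitual physical activity, and the titles of Tables 4 and 5 present their contents as the best variables. Readers will look there to see which predictors matter, and will take p<0.05 or a CI excluding zero as evidence at the 5% level. For the rows actually shown, that reading is usually too favourable, by an amount the SAP does not let anyone determine.

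**Working it through.** **No figure to reproduce.** The SAP gives no power or error-rate calculation for Models 2a and 2b. The only stated benchmarks are two-sided 0.05 and 95% CIs.

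**Inputs from the SAP.** Study size gives 78 children with CPUP data (Model 2a) and 123 with accelerometry (Model 2b, a maximum if the valid-wear-day rule is still to be applied). Tables 2 and 3 have 16 predictor rows each. Coding the multi-level items:
- Table 2: 16 + 1 (GMFCS, 3 levels) + 2 (subtype, 4 levels) + 3 (region, 5 levels) = 22 terms.
- Table 3: 16 + 1 (GMFCS) + 2 (FMS at 3 distances) + 3 (region) = 22 terms.

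**Assumptions not in the SAP.** Gaussian predictors with common correlation 0.3; 0 or 4 true predictors of equal effect; penalty at the minimum of 10-fold cross-validation; ordinary least squares refit of the retained variables on the same data.

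**Formulas.** For a noise variable:
- P(p<0.05 | retained) = P(retained and p<0.05) / P(retained).
- CI coverage given retention = 1 − P(p<0.05 given retention), because the true coefficient is zero.

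**Complete data, 1000 replicates per row:**

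| n | True R² | p<0.05 given retained | CI coverage | p<0.05 per candidate, after lasso | p<0.05 per candidate, no selection |
|---|---|---|---|---|---|
| 78 | 0 | 38.3% | 61.7% | 3.1% | 5.0% |
| 78 | 0.2 | 17.8% | 82.2% | 4.4% | 5.1% |
| 78 | 0.4 | 16.1% | 83.9% | 5.0% | 5.1% |
| 123 | 0 | 39.7% | 60.3% | 3.0% | 5.3% |
| 123 | 0.2 | 16.2% | 83.8% | 4.4% | 5.3% |
| 123 | 0.4 | 15.7% | 84.3% | 4.9% | 5.3% |

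The columns fit together. At n=78 and R² 0.2, the implied chance that a noise variable is retained is 0.044 / 0.178 = 0.25. About a quarter of noise variables are shown, and nearly all the false-significant ones are among them.

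**Cause.** A separate simulation with 16 terms (250 runs per scenario; correlation 0 or 0.3; no true effects, or three) gave 33–43% with no true effects and 14.5–18% with three. Refitting the same selected variables on fresh data of equal size gave 3.6–5.6%, and the full unselected model gave 4.5–5.8%. The excess therefore comes from selecting and testing on the same data.

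**With chained-equation imputation, the 50% rule and a Rubin-pooled refit** (20 imputations and 200 replicates, or 10 and 140 in the runs marked †, against the SAP's 100 imputations):

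| Outcome in imputation model | Missing | n | True R² | p<0.05 given retained | Unselected, per candidate |
|---|---|---|---|---|---|
| No | 10% | 78 | 0 / 0.2 / 0.4 | 41.6% / 7.5% / 5.2% | 0.5–1.8% |
| No | 10% | 123 | 0 / 0.2 / 0.4 | 48.9% / 8.0% / 6.0% | 0.5–1.8% |
| No | 20% | 78 | 0.2 | 4.0% | – |
| No† | 5% | 78 | 0.2 | 13.8% | 2.6% |
| Yes† | 10% | 78 | 0.2 | 12.9% | 4.3% |
| Yes† | 10% | 123 | 0.2 | 16.0% | 5.2% |

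In the six 10%-missing runs without the outcome, pooled tests were conservative before any selection. The smallest conditional rate over the largest unselected rate is 5.2 / 1.8 = 2.9, so selection still multiplies the rate about threefold or more.

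**Sensitivity, complete data.** Varying the correlation from 0 to 0.6 (R² 0 and 0.2) gave 13.6% to 46.0%. A one-standard-error penalty at R² 0.2 gave 39.2% (n=78) and 35.1% (n=123). Retained true predictors had CI coverage of 94–97% under the minimum-error penalty, but 84.9% and 87.4% under the one-standard-error penalty.

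**The case against.** The strongest reply has four parts.

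1. **The columns are inferred.** Tables 4 and 5 are not drawn, so likeness to Tables 2 and 3 might mean only the ICF layout. The sentence on alpha speaks of differences and means, which fits the group comparisons under Descriptive statistics. This stands as a limit: both the columns and the refit are the natural reading, not stated text. The alternative is no better. If the coefficients are penalized, ordinary CIs and p-values do not apply, and the SAP names no method to fill those columns.
2. **Nothing turns on these p-values.** Retention depends on inclusion proportion, performance on adjusted R-squared and RMSE, and the table titles disclose the selection. False-significant rows per candidate are no more frequent than in an unselected model. All true, and it confines the harm to misreading. But only retained rows are shown, so the conditional rate is the one that matters to a reader, and disclosing selection does not say that it affects the p-values.
3. **The largest figures need every candidate to be unrelated to activity.** In that complete-data setting the lasso retained nothing in 60% (n=78) and 63% (n=123) of 400 repeat runs each, so the table would usually be empty. This is fair, and the all-null figures should not lead.
4. **The closest match to the SAP is near nominal.** The imputation text does not name the outcome as included, and with 10–20% missing and true predictors present the rate was 4–8%. That stands as a number. It arises because conservative pooled tests offset the selection effect, and it rises to 13–16% if the outcome is included or to 13.8% if only 5% is missing.

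**Conclusion.** The concern holds. Following the SAP on its natural reading puts p-values and 95% CIs into Tables 4 and 5 whose error rates are not those implied, with no method or caveat to account for the selection.

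The size is uncertain. At correlation 0.3 with the cross-validated penalty, P(p<0.05) for a retained noise variable ranged from 4% to 49% against a nominal 5%. It was 16–18% with complete data and true predictors present, and 4–16% with imputation. These figures rest on assumed data, an assumed penalty rule and an inferred refit; the imputed runs are also small and use fewer imputations than planned. What is firm is the direction in most settings and the absence of any known error rate for a printed p-value.

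The problem is limited to secondary Models 2a and 2b. Selecting variables by lasso is legitimate in itself, and Model 1 (Tables 2 and 3) is unaffected.

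**What to change.** - **Tables 4 and 5:** remove the p-value column and the unadjusted 95% CIs. Show each retained predictor's coefficient and the proportion of imputation sets in which it was selected, which the Missing data procedure already produces.
- **If intervals are wanted:** use a bootstrap that repeats the whole procedure (impute, lasso, retention rule, refit). The retention cutoff must then be fixed in advance, because an elbow plot judged by eye cannot be repeated in every resample.
- **Minimum version:** keep the columns but label them as not adjusted for selection and descriptive only.
- **Section 4, Confidence intervals and p-values:** add that the 0.05 level does not apply to Models 2a and 2b.

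The cost is SAP wording and two table shells, or one footnote and one sentence for the minimum version. No new data are needed and the primary analysis does not change. The downside is that Models 2a and 2b carry no significance statements. The optional bootstrap takes real computing time, since each resample repeats 100 imputations and 100 lasso fits.
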